3.0 Study Objectives

3.1 Primary Objective:

3.1.1 To evaluate the preventative activity of DFMO as a single agent in patients that are in remission based on: Event free survival (EFS)

3.2 Secondary Objectives:

3.2.1 Correlation of urinary polyamine levels with progression of disease in neuroblastoma.

3.2.2 To evaluate the preventative activity of DFMO as a single agent in patients with neuroblastoma who are in remission based on:

- Overall Survival (OS)

3.2.3 To continue to determine the safety and tolerability of DFMO as a single agent and in pediatric and young adult patients with high risk neuroblastoma that is in remission.

3.2.4 To evaluate the pharmacokinetics (PK) of new DFMO formulation in a minimum of 10 patients.

3.2.5 Biological Correlates to minimally include: 1) Urine: polyamine levels and blood inflammatory markers, 2) Blood- microRNA analysis as predictor of DFMO effect; ODC SNP analysis in DNA isolated from nucleated cells; circulating tumor cell analysis, and explorative biomarker analysis 3) Bone Marrow- flow cytometry of minimal residual disease of tumor; explorative biomarker analysis

4.0 Study Design

This study is an open label, single agent, multicenter, study for patients with neuroblastoma that is in remission.

4.1 DFMO Treatment

In this study subjects will receive twenty-seven (27) cycles of oral DFMO at a dose of 500 to 1000 mg/m² BID (per dosing chart in section 6.1.2) on each day of a 28 day cycle. DFMO is provided as 250mg tablets.

4.2 Response Evaluations

At the times indicated in Section 7.0 and the Table of Procedures and Assessments, scans will be obtained to evaluate response for subjects enrolled in this study. Response will be assessed to evaluate the potential benefit of DFMO in this patient population.

4.3 Pharmacokinetic Evaluations

Plasma concentrations of DFMO will be determined for a minimum of 10 currently enrolled subjects on their last day of taking the DFMO tablet formulation and on Days 2-5 post start of taking the new formulation at hours 0 (pre dose), 30min, 1 hour, 3 hours, and 6 hours post-dose. Change from old formulation to new formulation may take place on any day of any cycle after subject consents to new formulation.

4.4 Biological Studies

These studies will evaluate the level of polyamines and inflammatory markers in urine. Subjects will have an opportunity to participate in additional correlative biological studies on a voluntary basis to evaluate the level of polyamines and inflammatory markers in blood. These voluntary studies will evaluate microRNA levels in blood and ODC activity in white blood cells. They will also evaluate minimal residual disease in bone marrow. These biologic studies may be able to contribute to our knowledge of molecular determinants of response to therapy and/or the development of biomarkers to help guide future therapy.

5.0 Patient Selection

Eligibility:

5.1 Inclusion Criteria:

1. Age: 0-21 years at the time of diagnosis.
2. Diagnosis: histologic verification at either the time of original diagnosis or a previous relapse of high risk neuroblastoma.
3. Disease Status: Neuroblastoma that is in remission
4. Greater than 30 days from completion of cytotoxic and antibody therapy and less than 120 days from previous therapy
5. A negative serum or urine pregnancy test is required for female subjects of child bearing potential (onset of menses or ≥ 13 years of age).
6. Both male and female post-pubertal study subjects need to agree to use one of the more effective birth control methods during treatment and for six months after treatment is stopped. These methods include total abstinence (no sex), oral contraceptives (“the pill”), an intrauterine device (IUD), levonorgestrol implants (Norplant), or medroxyprogesterone acetate injections (Depo-provera shots). If one of these cannot be used, contraceptive foam with a condom is recommended.
7. ANC $> 500/\mu\text{l}$ and platelet count $> 50,000/\mu\text{l}$
8. Organ Function Requirements: Subjects must have adequate liver function as defined by:
 - a. AST and ALT $< 10\times$ upper limit of normal
 - b. Serum bilirubin must be ≤ 2.0 mg/dl
 - c. Serum creatinine based on age/gender as follows:

Age	Maximum Serum Creatinine (mg/dL)	
	Male	Female
1 month to < 6 months	0.4	0.4
6 months to < 1 year	0.5	0.5
1 to < 2 years	0.6	0.6
2 to < 6 year	0.8	0.8
6 to < 10 years	1	1
10 to < 13 years	1.2	1.2
13 to < 16 years	1.5	1.4
≥ 16 years	1.7	1.4

9. Informed Consent: All subjects and/or legal guardians must sign informed written consent. Assent, when appropriate, will be obtained according to institutional guidelines

5.2 Exclusion Criteria:

1. Lansky score < 60%
2. BSA (m²) of <0.25
3. Investigational Drugs: Subjects who are currently receiving another investigational drug are excluded from participation.
4. Anti-cancer Agents: Subjects who are currently receiving other anticancer agents are not eligible. Subjects must have fully recovered from the effects of prior chemotherapy (hematological and bone marrow suppression effects).
5. Infection: Subjects who have an uncontrolled infection are not eligible until the infection is judged to be well controlled in the opinion of the investigator.
6. Subjects who, in the opinion of the investigator, may not be able to comply with the safety monitoring requirements of the study, or in whom compliance is likely to be suboptimal, should be excluded.

Additional criteria:

Subjects willing to participate in the correlative biologic studies will sign an additional consent form to provide bone marrow and blood for analysis.

- Stratum 1: Subjects that are in remission at the end of upfront therapy defined as chemotherapy (5-7 cycles), surgery as indicated, consolidation therapy as indicated, radiation therapy as indicated, anti-GD2 antibody therapy with retinoic acid up to 6 cycles.
- Stratum 2: Subjects that are in remission after any previous relapse or refractory therapy

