Based upon tabled median EFS times all patients presented by Santana et al. (Cancer, June 15, 2008) for first and second recurrence times, a median first recurrence time of 8.7 months is equivalent to a 14.8% EFS at two years, and the median time to a subsequent second recurrence of 3.8 months is equivalent to an EFS rate of 1.3% at two years assuming an exponential time-to-event model. Assuming that two thirds of the relapse patient population will have had only a single relapse and that the other third of the patients will have had two or more relapses, then a weighted average of these two EFS rates (14.8% and 1.3%) equals 10.3%. A 10% historical EFS rate for two years was assumed for simplicity. Examination of an increase in EFS will require a sample size of n = 33 subjects in Stratum 2 to test whether treatment with DFMO can prolong the overall estimated EFS at two years to 30% from the 10% two years estimate for the above historical data in this patient population. The sample size is based upon a one sample binomial test of proportions with a power 80% and a 5% two -tailed Type I error level.

An observation of 7 or more patients with at least a two year EFS rate out of the $n = 33$ patients will result in the rejection of the null hypothesis of a 10% EFS in favor of the alternative of a 30% two year EFS rate. An exact binomial 95% confidence interval for the two year estimated EFS will complement the prior formal two-stage hypothesis test. Since the actual EFS time-to-event data is derived from the times to recurrence, a Kaplan-Meier analysis of the time-to-event data analysis will be conducted, and the median time to recurrence and a 95% confidence for this value will be obtained to supplement this EFS point estimate. Since this group of Stratum 2 patients will consist of patients with prior single and multiple recurrence histories, EFS and time to event data will be examined by prior recurrence histories. In particular, the impact of prior recurrence history on the time to recurrence will be explored using Kaplan-Meier analysis and Cox proportional hazard models. The response to DFMO therapy and subsequent recurrences will also be explored in combination with prior recurrence histories using Cox models.

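### Stratum 2 admits never-relapsed patients in remission after refractory therapy, but its 10% null and recurrence-history analysis cover only relapsed patients

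*Combined protocol and SAP*

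**What the plan says.** The additional criteria in Section 5.2, repeated in the synopsis, define the stratum as "Stratum 2: Subjects that are in remission after any previous relapse or refractory therapy". Refractory therapy is enough on its own. No other criterion requires a relapse: the histology criterion in Section 5.1 accepts "histologic verification at either the time of original diagnosis or a previous relapse of high risk neuroblastoma".

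The Stratum 2 text under Sample Size and Analysis in Section 10 derives the null from two groups:

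- one relapse: "a median first recurrence time of 8.7 months is equivalent to a 14.8% EFS at two years";
- two or more relapses: "the median time to a subsequent second recurrence of 3.8 months is equivalent to an EFS rate of 1.3% at two years".

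The weights rest on the assumption that "two thirds of the relapse patient population will have had only a single relapse", with the remaining third having had two or more. The result, 10.3%, is rounded to 10%. The test rejects 10% in favour of 30% if at least 7 of 33 patients are event-free at two years.

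The same text introduces the subgroup analysis with "Since this group of Stratum 2 patients will consist of patients with prior single and multiple recurrence histories", and plans Kaplan-Meier and Cox analyses by that history. Nowhere is there a rate, expected share, cap, separate null or sensitivity analysis for patients with no prior recurrence.

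**The concern.** Stratum 2 has no concurrent control, so its test means only what the comparability of the 33 patients with the historical source allows. Eligibility and benchmark describe different populations. A patient with zero relapses has no weight in the null, and no re-weighting of single against multiple relapses can supply one.

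If such patients do better than 10% at two years without DFMO, the test can reject with an inactive drug. If they do worse, the test is biased against the drug. Either way, a pass or a fail could not be attributed cleanly to DFMO, and the planned recurrence-history analysis has no category that would reveal the problem.

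**Working it through.** **Inputs from Section 10 and the synopsis.** Medians 8.7 and 3.8 months; weights 2/3 and 1/3; p0 = 10%, p1 = 30%; n = 33; reject at 7 or more; 80% power; 5% two-tailed.

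**Assumed inputs, not in the documents.** k = number of never-relapsed refractory patients among the 33; q = their two-year EFS without DFMO.

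**1. Reproduce the null** (exponential model, S(24) = 0.5^(24/median)).

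- 0.5^(24/8.7) = 14.8%
- 0.5^(24/3.8) = 1.3%
- 2/3 × 14.8% + 1/3 × 1.3% = 10.3%

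The plan's figure reproduces. The weights sum to 1, so zero-relapse patients have weight 0.

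**2. Reproduce the test** (exact binomial, n = 33).

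- Cut-off 7: P(X ≥ 7 | 10%) = 4.17%; power at 30% = 90.6%.
- Cut-off 8: P(X ≥ 8 | 10%) = 1.41%; power at 30% = 81.8%.

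The printed cut-off has little slack. P(X ≥ 7) is 4.8% at the unrounded 10.3%, and it passes 5% once a common no-effect rate exceeds about 10.4%.

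**3. Add k never-relapsed patients, no DFMO effect.** X = Bin(33 − k, 0.10) + Bin(k, q), and the upper tail comes from the exact convolution. P(X ≥ 7):

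| k | q = 5% | q = 10% | q = 20% | q = 30% | q = 50% |
|---|---|---|---|---|---|
| 0 | 4.2% | 4.2% | 4.2% | 4.2% | 4.2% |
| 3 | 3.3% | 4.2% | 6.1% | 8.4% | 14.1% |
| 7 | 2.4% | 4.2% | 9.5% | 17.5% | 40.7% |

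The turning point is q = 10%: below it the false-positive risk falls, above it the risk rises. If never-relapsed patients did only as well as the plan's single-relapse group (q = 14.8%), k = 3 would already give 5.05%.

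**4. Same calculation at a cut-off of 8.**

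- k = 3: 2.2% (q = 20%) and 3.3% (q = 30%).
- k = 7: 3.9% (q = 20%), 8.2% (q = 30%) and 23.7% (q = 50%).

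A higher cut-off reduces the problem but does not remove it.

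**5. Power if the test is limited to relapsed patients** (smallest cut-off with an upper tail of at most 2.5% at 10%).

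| n relapsed | Cut-off | Upper tail at 10% | Power at 30% |
|---|---|---|---|
| 33 | 8 | 1.4% | 82% |
| 28 | 7 | 1.8% | 78% |
| 26 | 7 | 1.2% | 70% |
| 23 | 6 | 2.3% | 73% |

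Power does not fall smoothly with n because the cut-off is a whole number.

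**The case against.** The strongest reply is that the statistical text shows what was intended. It describes the stratum by recurrence history, and Section 1.0 motivates the study partly with relapsed patients in second remission. On that reading the refractory branch is loose wording, and aligning the sections would be enough. Intent is a fair inference, but eligibility is what sites apply, and as written it admits these patients. The planned exact confidence interval, Kaplan-Meier and Cox analyses could help show heterogeneity if zero-recurrence patients were coded, but they do not repair the binomial test.

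A second reply is that the direction of bias is unproven. That stands. With q at or below 10% there is no inflation: k = 10 with q = 5% gives 1.8%. Part of the inflation seen at a cut-off of 7 also reflects the thin margin of that cut-off rather than the mixed population.

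Three stronger readings are tempting and are not supported:

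- **That these patients will make an inactive drug look active.** This needs q above 10%, which the documents do not give. The 70% figure cannot stand in for q: it is the Stratum 1 baseline, for remission at the end of upfront therapy, and is not stated for patients who needed refractory therapy.
- **That the strata overlap.** Stratum 1 is "Stratum 1: Subjects that are in remission at the end of upfront therapy defined as chemotherapy (5-7 cycles), surgery as indicated" and further listed components. Overlap would require counting refractory cycles within the upfront 5-7, which the text does not say.
- **That a site can choose the stratum with the lower bar.** Section 7.1 requires lead-site confirmation based on subject data. It is silent on stratum assignment, but nothing gives sites a free choice.

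**Conclusion.** The mismatch is real and unreconciled. Eligibility in the synopsis and Section 5.2 includes never-relapsed refractory patients, while the null and the recurrence-history analysis in Section 10 do not. It affects the only formal Stratum 2 test.

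Its size and direction are unknown because k and q are undocumented. The working assumes relapsed patients at exactly 10%, no DFMO effect and independent outcomes. On that basis, three such patients move the rejection probability from 4.2% to between 3.3% and 8.4% for q from 5% to 30%. Seven move it to between 2.4% and 40.7% for q from 5% to 50%. The supported statement is that the test can mislead in either direction, not that it will favour DFMO.

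**What to change.** Reconcile the stratum definition in the synopsis and Section 5.2 with the Stratum 2 text in Section 10, before outcomes are examined:

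1. Limit the formal binomial test to patients with at least one documented relapse before the current remission, the population from which 10% was derived. The criterion should be relapse alone. Adding progression would readmit refractory patients who progressed without relapsing, for whom the null again has no rate.
2. Report never-relapsed refractory patients as a separate descriptive group, tested against neither 10% nor 70%.
3. Record the number of prior relapses, including zero, and add a no-prior-recurrence category to the recurrence-history analysis.
4. If fewer than 33 relapsed patients are evaluable, recompute the exact cut-off for the number available and restate the power.

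The cost is amendment wording, one data field and fewer patients in the test. With 2.5% in the upper tail, power at 30% falls from 82% (n = 33) to about 78% (n = 28) and 70% (n = 26). Cost and benefit move together: if few never-relapsed patients enrol, little power is lost, and the distortion removed is usually modest too, unless q is well above 10%.

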6.0 STUDY DRUG ADMINISTRATION

6.1 DFMO

6.1.1 Description, Formulation, and Storage of DFMO

The dosage form to be used in this study are provided as a convex tablet containing 250 mg of eflornithine HCl, monohydrate. The tablets are packaged and sealed in opaque white HDPE bottles, and each bottle contains 100 tablets.

The tablets are to be stored at room temperature (20-25⁰C).

6.1.2 DFMO Dosing Table Per Weight Group:

The following table will be used to determine dispensing of DFMO.

DFMO Dose:

BSA (m ²)	Tablets to be Dispensed for each dose	Total Tablets Per Day	Actual Mg/m ²
>1.5	Four (4) tablets orally twice a day	Eight (8)	625 and down per dose
0.75 to 1.5	Three (3) tablets orally twice a day	Six (6)	500 to 1000 per dose
0.5 to < 0.75	Two (2) tablets orally twice a day	Four (4)	675 to 1000 per dose
0.25 to < 0.5	One (1) tablet orally twice a day	Two (2)	500 to 1000 per dose
<0.25	Not eligible for trial		

6.1.3 Administration of DFMO

Treatment will be administered on an outpatient basis unless hospitalization is required for another reason.

Each entire dose of DFMO tablets should be swallowed.

Subjects will be advised to maintain a low Polyamine diet during the duration of this study. A handout will be provided to subjects with foods they should avoid while on this study.

Subjects will be given a ‘patient instruction sheet’ for home administration.

Subjects will be given a ‘dosing diary’ to keep track of doses given at home.

6.1.4 Subjects Unable to Swallow Tablets

For subjects unable to swallow tablets, DFMO tablets may be chewed or crushed in a teaspoon and administered with a small amount of liquid. Note, tablets may not completely dissolve.

Recommended liquids for mixing (to cover taste)- Lemonade, Apple, Cranberry, Grape, or Pineapple

DFMO may NOT be mixed in high polyamine juices such as orange or grapefruit juice.

Crushed DFMO tablets may also be mixed in 1-2 tablespoons of chocolate syrup or apple sauce. The DFMO tablets will not dissolve, and this is acceptable. This technique is simply to mask the flavor.

6.1.5 Missed Doses

If a subject vomits or misses a dose they should skip the missed dose and continue the drug at the next dose. Do not make up missed doses.

6.1.6 DFMO Clinical Pharmacology

DFMO (Eflornithine hydrochloride) is a member of the following drug classes: 1) inhibitor of ornithine decarboxylase (ODC), 2) hirsutism (excess hair growth) retardant, and 3) antiprotozoals. Eflornithine is FDA approved as a cream for treatment of female hirsutism, and in intravenous form for treatment of trypanosomiasis. The oral tablet form is not available outside of the clinical trial setting in the U. [REDACTED]

Contraindications: Prior hypersensitivity to eflornithine.

Common side effects:

Overall, the most frequently reported AEs in NCI, DCP-sponsored chemoprevention studies were diarrhea (9.0%), headache (7.5%), nausea (6.5%), hearing loss (5.6%), tinnitus (4.3%) and asthenia (4.7%). Other common toxicities (each accounting for 2 to 3% of all AEs reported) were epigastric pain, flatulence, dyspepsia, anemia, dizziness and skin rash. Less common toxicities (each accounting for 1 to 2% of all AEs reported) were: stomatitis, rhinitis, insomnia, infections, vomiting, vasodilation, dry mouth, constipation, dry skin, menstrual disorders, pharyngitis, emotional lability, pruritis, myalgia, and pain (miscellaneous). The most significant adverse effects associated with clinical administration of DFMO in chemoprevention trials are loss of hearing acuity and tinnitus. These effects have generally been found to be reversible when DFMO treatment is stopped. Patients who receive a cumulative oral dose of DFMO below 150 g/m² experience minimal ototoxicity.

Infrequent side effects: Hearing loss/change by audiometry testing has been reported in 8.4% of patients on high dose eflornithine. Rash and alopecia have been reported in 3% of patients. Anorexia and abdominal pain have been reported in 2% of patients treated with eflornithine.

Rare but serious side effects include dizziness (1%), headaches (2%), and seizures (8%), have been reported in patients on intravenous eflornithine. Myelosuppression (including leukopenia, [37%], anemia [55%], and thrombocytopenia [14%]) has been reported at high intravenous doses, but does not usually occur at the low dose (500 mg) utilized in this study.

Pregnancy and Lactation: Pregnancy category C. It is unknown if eflornithine crosses the placenta. Case reports in humans along with animal studies (mice, rats) indicate potential for fetotoxicity. Experiments in rodents indicate that eflornithine blocks yolk sac formation and trophoblast differentiation, affecting processes such as vasculogenesis and steroidogenesis (Lopez-

Garcia, *et al.*, 2008). The World Health Organization has not determined a breast feeding rating for eflornithine due to insufficient data. The Thompson lactation rating is that infant risk cannot be ruled out. No studies investigating the safety of lactation after eflornithine administration have been conducted, nor are there data to determine drug levels in breast milk after drug administration.

Toxicity for DFMO Potential Risk:

Likely Happens to 10-30 patients out of every 100
	
Less Likely Happens to 3-10 patients out of every 100
	
Rare Happens to fewer than 3 patients out of every 100

 • Fewer red and white blood cells 
 ○ a low number of red blood cells can make you feel tired and weak and may require transfusion. ○ a low number of white blood cells can make it easier to get infections • Decrease in the number of platelets made in the bone marrow 	
 • Nausea • Hearing Loss • Ringing in ears • Diarrhea • Headache • Weakness 	
 • Loss of appetite • Abdominal Pain • Flatulence (gas) • Dizziness • • Skin Rash • Seizures • Sores in the mouth • Runny nose • Difficulty sleeping • Infections • Dry mouth • Constipation • Dry skin • Menstrual disorders • Sore throat • Vomiting • Vasodilation (the relaxation of blood vessels possibly causing low blood pressure) • Emotional ups and downs • Itchiness • Body aches • Pain

Four particular areas of concern have been identified with regard to the safety of subjects participating in this study and an attempt to address each of them is outlined below: The main considerations are: thrombocytopenia, hearing loss, gastrointestinal and non-G.I. side effects.

a) DFMO Specific Adverse Events

(1) Hearing loss.

Although hearing loss has been a problem at higher doses (see below), clinical changes in hearing have been uncommon (one of 123 subjects in the phase IIb trial) and reversible in the doses proposed for this trial (62). An extended analysis of these observations is in press (65). There was no statistically significant shifts in distortion product otoacoustic emission levels. For

auditory pure tone thresholds, there was a subtle 2-3 dB decrease in hearing sensitivity for the two higher DFMO doses (0.2 and 0.4 gm/M²/day), but only for the two lowest frequencies at 250 and 500 HZ. However in two phase I trials using lower doses of DFMO, done by other investigators, no audiometric changes were seen after approximately 6 months of DFMO therapy at 0.50Gm/m²/d (total dose 90Gm) although some changes were seen at higher doses (79). Hearing loss may occur in association with DFMO administration at high doses. In a meta-analysis of previous studies, (64), it was reported that less than 10% of the subjects who received cumulative doses below 150 Gm/m² developed a demonstrable hearing deficit, while hearing losses were observed in up to 75% of subjects who received cumulative doses above 250 Gm/m². This side effect was thought to be totally reversible upon drug discontinuation. Some study participants taking DFMO at doses similar to those used in this study have experienced mild decreases in hearing soft sounds. These changes have been uncommon and usually subclinical (that is, noticeable on special hearing tests called audiograms, but not in normal conversation or daily activities). Although an affected participant's level of hearing usually returns to its usual state when drug is stopped, in a small percentage of cases (occurring in less than 5% of participants taking the drug) effects have persisted even after drug was stopped. These changes are most likely not reversible in all subjects. However, in a recently completed phase IIb trial of DFMO audiologic changes that were clinically significant were not detected, even in the highest dose group (0.4Gm/m²/day) (extended analysis, 65). It is probable that at low doses of DFMO ongoing recovery of inner ear polyamines occurs and clinical hearing loss will be rarely, if ever, seen. Since hearing loss is usually totally reversible after drug discontinuation, this approach appears safe and cost effective.

(2) Thrombocytopenia (low platelets)

Thrombocytopenia has been reported predominantly in studies using “therapeutic” doses of DFMO (>3Gm/m²/day) and primarily in cancer patients who had previously undergone chemotherapy or patients with compromised bone marrow. Other side effects ascribed to DFMO have been rare and, to date, seen only at high doses.

(3) Other

Skin rash, anemia, and neutropenia have also been seen with DFMO administration

(4) GI

Abdominal pain, loss of appetite, diarrhea have been reported.

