Specific experience with DFMO and studies in patients with adenomatous polyps are described in four clinical chemoprevention studies that have been performed (59, 60, 61, 62)

Boyle JO et al in a pilot study established that DFMO could lower polyamine content in colorectal mucosa. They demonstrated that shed oral extracellular mucosal cells did not provide a reliable surrogate estimate of DFMO effects on the colon. Meyskens et al performed a dose de-escalation chemoprevention trial of 2 difluoromethylornithine in patients with colon polyps. The short-term (one month) Phase IIa study established that DFMO was both safe and effective in reducing colorectal mucosal polyamine contents when administered orally to patients as low as .25 gm/m² for 28 days. No ototoxicity was observed at doses up to twice this amount. They

demonstrated that both putrescine content and the ratio of spermidine to spermine and changes in these parameters as a function of DFMO treatment decreased as a function of donor age, which is an important consideration in the evaluation of DFMO effect. Meyksens then showed in an intermediate term (12 months) Phase IIb clinical chemoprevention trial demonstrated that polyamine levels in rectal mucosa can be continually suppressed by daily oral doses of DFMO that produced few or no side effects (62). Using a similar design, a smaller study has confirmed these results (63); this trial reported some reversible ototoxicity (at a dose of DFMO of 500 mg/m²/day).

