Usage of DFMO at high doses for therapeutic purposes indicated that hearing loss occurred and seemed to be related to the total dose; this toxicity was however reversible (64). The toxicity of low dose DFMO has been assessed in both a phase IIa and phase IIb trial and the evaluation of hearing changes was described in the phase IIb trial (65). They were unable to demonstrate an effect of DFMO on otoacoustic emissions at any dose of DFMO (0, -75, 200, 400 mg/m²/day) administered. They detected a subtle decrease in pure tone threshold that was dose-related. However, even at the highest dose the decrease was less than 4 db. Since 1-2 db decreases per year of hearing in normal humans in this age range have now been shown (66,67), results should not raise undue concern since: (1) the effects of DFMO on hearing loss are known to be rapidly reversible after discontinuation of the drug and (2) 10-20 db losses need to occur before the effect is clinically evident. Nevertheless, all participants will receive a baseline audiogram, will be checked throughout the study and if clinically indicated.

Summary

These studies suggest that ODC/polyamines are critical in oncogenesis and therefore present a therapeutic target for the treatment and prevention of recurrence of NB and other types of cancer. This study will focus on the use of DFMO in high risk neuroblastoma patients that are in remission as a strategy to prevent recurrence.

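### Section 6.1.6 reassures on hearing from a trial that gave at most 0.4 g/m²/day for 12 months, as if those were this trial's doses; the plan here is 1–2 g/m²/day for 756 days, and its cumulative total is never stated

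*Combined protocol and SAP*

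**What the plan says.** The hearing-loss paragraph of section 6.1.6 concedes a problem at higher doses. It then says that clinical changes were uncommon, one of 123 subjects in the phase IIb trial, and "reversible in the doses proposed for this trial (62"). It adds three further reassurances:

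- In phase I work at 0.50 g/m²/day, "no audiometric changes were seen after approximately 6 months of DFMO therapy".
- In the phase IIb trial, "audiologic changes that were clinically significant were not detected, even in the highest dose group", which was 0.4 g/m²/day.
- A later sentence describes mild hearing changes in people whose doses it calls similar to this study's. The paragraph then concludes that at low doses clinical hearing loss should hardly occur.

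Section 2.1 describes the phase IIb study as an "intermediate term (12 months) Phase IIb clinical chemoprevention trial".

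The same paragraph also reports a meta-analysis with a hearing deficit in fewer than 10% of subjects below 150 g/m², while "hearing losses were observed in up to 75% of subjects who received cumulative doses above 250" g/m². On recovery it says: "These changes are most likely not reversible in all subjects". The risk table in 6.1.6 puts hearing loss at 3–10 per 100.

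Sections 4.1 and 6.1.2 set the dose at 500–1000 mg/m² twice daily, and section 7.8 gives 756 days of treatment. Section 7.5 schedules audiograms at the end of cycles 6, 12 and 27 and for any suspected loss. The safety data listed in section 10.3 are hematology, chemistry, vital signs and adverse events. Section 8.2 records events of Grade 2 or higher.

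**The concern.** A reader told that this trial's doses are those of the phase IIb trial will place it below the 150 g/m² level. The dosing table and treatment duration place it well above 250 g/m² for anyone who completes treatment at full dose. The section ties ototoxicity to cumulative dose but does not apply that measure to its own regimen.

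Section 3.2.3 makes this a stated objective: "To continue to determine the safety and tolerability of DFMO as a single agent". Hearing loss is also one of four named areas of safety concern. Section 6.1.6 says that hearing changes are mostly subclinical and visible on audiograms. Followed literally, section 10.3 does not list audiograms, and a change below Grade 2 need not be recorded as an adverse event. The serial audiograms could therefore stay out of the safety report, although they are taken at exposures that the cited low-dose trials did not reach.

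**Working it through.** **Inputs.** Tablets of 250 mg and the BSA bands come from section 6.1.2, the 27 cycles of 28 days from 4.1 and 7.8, and the audiogram times from 7.5. The phase IIb duration is in 2.1. Its top dose and the 150 and 250 g/m² levels are in 6.1.6.

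**The plan's own figures.** 27 × 28 = 756 days, as in 7.8. The phase I total of 90 g in 6.1.6 reproduces as 0.5 g/m²/day × 180 days = 90 g/m².

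**Cited exposure.** Phase IIb maximum: 0.4 × 365 = 146 g/m². The documents do not print this product.

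**Planned daily dose, from tablet counts (both daily doses):**

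| BSA (m²) | g/day | g/m²/day |
|---|---|---|
| 0.25 to <0.5 | 0.5 | 2.0 down to just above 1.0 |
| 0.5 to <0.75 | 1.0 | 2.0 down to 1.33 |
| 0.75 to 1.5 | 1.5 | 2.0 down to 1.0 |
| >1.5 to 2.0 | 2.0 | 1.33 down to 1.0 |

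The range is 1–2 g/m²/day for BSA up to 2.0 m².

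**Comparison at full dosing:**

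- Daily dose ratio: 1/0.4 = 2.5 to 2/0.4 = 5.
- Full course: 1 × 756 = 756 to 2 × 756 = 1512 g/m².
- Cumulative ratio: 756/146 = 5.2 to 1512/146 = 10.4.
- 150 g/m² is reached at 150/2 = day 75 to 150/1 = day 150.
- 250 g/m² is reached at 250/2 = day 125 to 250/1 = day 250.

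**Exposure at the scheduled audiograms, full dosing:**

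| Time | Day | g/m² |
|---|---|---|
| End of cycle 6 | 168 | 168–336 |
| End of cycle 6, with ±14 days | 154–182 | 154–364 |
| End of cycle 12 | 336 | 336–672 |
| End of cycle 27 | 756 | 756–1512 |

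**Cases that lower it:**

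- BSA 2.2 m²: 2.0/2.2 = 0.909 g/m²/day. The course is 687 g/m², 250 g/m² is passed at day 275, and day 154 gives 140 g/m².
- One step down throughout at BSA 1.5 m²: 1.0/1.5 = 0.667 g/m²/day. The course is 504 g/m², and 250 g/m² is passed at day 375.
- One tablet a day throughout at BSA 2.0 m²: 0.25/2.0 = 0.125 g/m²/day, or 94.5 g/m². Neither level is reached.
- Missed doses: at 1 g/m²/day, eight missed days bring 154 down to 146 g/m², so the earliest audiogram no longer exceeds the phase IIb maximum.

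**The case against.** **Disclosure.** Section 6.1.6 gives both cumulative levels, the 75% figure, persistence in under 5% of participants and incomplete reversibility. Dose and duration are stated elsewhere, so the total is one multiplication away. This stands, and a reader who inferred that the protocol conceals the hazard would be wrong. It does not repair a sentence that assigns this trial to the wrong dose range.

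**Cumulative dose is not the only measure.** The protocol also reports hearing by daily dose and argues that the inner ear recovers at low daily rates. Section 2.1 describes the background to the cumulative-dose result this way: "Usage of DFMO at high doses for therapeutic purposes indicated that hearing loss occurred and seemed to be related to the total dose". Section 6.1.6 places therapeutic dosing above 3 g/m²/day, higher than the plan here. The daily rates behind the 150 and 250 g/m² levels are not given, so the day counts may not carry over. This also stands. A reader might infer that up to three quarters of these children will lose hearing, and the documents do not support that. Nor do they show that low-rate recovery extends to 1–2 g/m²/day: section 2.1 reports some reversible ototoxicity at 500 mg/m²/day, and 6.1.6 notes some changes above 0.50 g/m²/day.

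**The 3–10% category.** The incidence figures in 6.1.6, 5.6% in chemoprevention studies and 8.4% on high-dose eflornithine, both lie inside it. A reader might conclude that the category is wrong, but no replacement rate can be drawn from the documents. Only a caveat is supportable.

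**Safeguards and reporting.** Related Grade 3 hearing toxicity would trigger a hold and dose reduction under 6.3. The safety officer reviews all adverse events, and the monitoring board meets every 6 months. The list in 10.3 need not be exhaustive, the synopsis promises the frequency of all adverse events, and 8.2 also mentions worsening from baseline. So it cannot be said that audiogram findings will go unreported, only that no summary of them is specified.

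**Conclusion.** The concern holds in this limited form. Section 6.1.6 twice equates this trial's doses with lower ones, and the text available for review never states the planned total of 756–1512 g/m² or compares it with 150 and 250 g/m². Section 2.2 appears in the table of contents but not in that text. Other dose data may sit there, but they could not make 0.4 g/m²/day equal to 1–2 g/m²/day.

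The figures assume full dosing and BSA up to 2.0 m². Dose reductions, missed doses, early stopping or larger BSA lower them, and at the lowest reduced dose neither level may be reached. A reader might infer that every first on-treatment audiogram falls beyond the low-dose evidence; that is true only at near-full dosing. The actual hearing risk at this regimen is unknown.

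The correction should be made because a safety statement is wrong as written and the audiograms have no specified analysis. The primary event-free survival analysis is unaffected.

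**What to change.** 1. **Section 6.1.6, wording.** Correct both statements that equate the doses: the one citing reference 62 and the later one calling earlier participants' doses similar to this study's. Limit the conclusion that clinical hearing loss should hardly occur to the cited low-dose trials, at most 0.4–0.5 g/m²/day. Keep the sentence on incomplete reversibility.
2. **Section 6.1.6, exposure.** State that full dosing with BSA up to 2.0 m² gives 756–1512 g/m², passing 150 g/m² by day 75–150 and 250 g/m² by day 125–250, and later or never with dose reductions, missed doses or larger BSA. Add that the daily rates behind those levels are not given, so the risk at this regimen is uncertain. Keep the 3–10% category, with a footnote that the risk at this exposure may be higher and that 75% is a cited maximum.
3. **Section 10.** Name audiograms among the safety data. Add a descriptive summary of hearing adverse events and of audiogram change from baseline against cumulative g/m² received, at the end of cycles 6, 12 and 27, with unscheduled audiograms shown separately. Define what counts as a hearing change. Note that dose and time on treatment rise together, so the summary cannot separate them.

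**Cost.** The risk statement becomes less favourable and one table is added. The plan schedules audiograms but does not say that results are entered in the case report form, so new data fields may be needed for tests already done. Dose, schedule, holds and reductions, board review and the event-free survival test stay as they are.
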